7.3 Subject Population(s) for Analysis

All-treated population: Any subject randomized into the study that received study drug.

8 Safety and Adverse Events

8.1 Definitions

Unanticipated Problems Involving Risk to Subjects or Others (UPIRTSO)

Any unanticipated problem or adverse event that meets the following three criteria:

- Serious: Serious problems or events that results in significant harm, (which may be physical, psychological, financial, social, economic, or legal) or increased risk for the subject or others (including individuals who are not research subjects). These include: (1) death; (2) life threatening adverse experience; (3) hospitalization - inpatient, new, or prolonged; (4) disability/incapacity - persistent or significant; (5) birth defect/anomaly; (6) breach of confidentiality and (7) other problems, events, or new information (i.e. publications, DSMB reports, interim findings, product labeling change) that in the opinion of the local investigator may adversely affect the rights, safety, or welfare of the subjects or others, or substantially compromise the research data, **AND**
- Unanticipated: (i.e., unexpected) problems or events are those that are not already described as potential risks in the protocol, consent document, not listed in the Investigator's Brochure, or not part of an underlying disease. A problem or event is "unanticipated" when it was unforeseeable at the time of its occurrence. A problem or event is "unanticipated" when it occurs at an increased frequency or at an increased severity than expected, **AND**
- Related: A problem or event is "related" if it is possibly related to the research procedures.

Adverse Event

An untoward or undesirable experience associated with the use of a medical product (i.e. drug, device, biologic) in a patient or research subject.

Serious Adverse Event

Adverse events are classified as serious or non-serious. Serious problems/events can be well defined and include;

- death
- life threatening adverse experience
- hospitalization
- inpatient, new, or prolonged; disability/incapacity
- persistent or significant birth defect/anomaly

or other events that in the opinion of the sponsor-investigator may have adversely affected the rights, safety, or welfare of the subjects or others, or substantially compromised the research data.

All adverse events that do not meet any of the criteria for serious, should be regarded as **non-serious adverse events**.

Adverse Event Reporting Period

For this study, the study treatment follow-up period is 12 months after enrollment. The adverse event monitoring period will end at the end of the follow-up period. If an event is reported after this time it would not be considered study related.

Preexisting Condition

A preexisting condition is one that is present at the start of the study. A preexisting condition should be recorded as an adverse event if the frequency, intensity, or the character of the condition worsens during the study period.

General Physical Examination Findings

At screening, any clinically significant abnormality should be recorded as a preexisting condition. At the end of the study, any new clinically significant findings/abnormalities that meet the definition of an adverse event must also be recorded and documented as an adverse event.

Post-study Adverse Event

All unresolved adverse events should be followed by the sponsor-investigator until the events are resolved, the subject is lost to follow-up, or the adverse event is otherwise explained. At the last scheduled visit, the sponsor-investigator should instruct each subject to report, to the sponsor-investigator, any subsequent event(s) that the subject, or the subject's personal physician, believes might reasonably be related to participation in this study.

Abnormal Laboratory Values

A clinical laboratory abnormality should be documented as an adverse event if it was exhibited as a severe reaction i.e. swelling, that required hospitalization or additional clinical intervention.

Hospitalization, Prolonged Hospitalization or Surgery

Any adverse event that results in hospitalization or prolonged hospitalization should be documented and reported as a serious adverse event unless specifically instructed otherwise in this protocol. Any condition responsible for surgery should be documented as an adverse event if the condition meets the criteria for an adverse event.

Neither the condition, hospitalization, prolonged hospitalization, nor surgery are reported as an adverse event in the following circumstances:

- Hospitalization or prolonged hospitalization for diagnostic or elective surgical procedures for a preexisting condition. Surgery should **not** be reported as an outcome of an adverse event if the purpose of the surgery was elective or diagnostic and the outcome was uneventful.
- Hospitalization or prolonged hospitalization required to allow efficacy measurement for the study.
- Hospitalization or prolonged hospitalization for therapy of the target disease of the study, unless it is a worsening or increase in frequency of hospital admissions as judged by the clinical investigator.

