8.2 Recording of Adverse Events

All adverse events will be documented as required under 21 CFR part 1271. Depending on the nature and seriousness of the adverse reaction, the IRB will be notified according to the Mayo Clinic IRB policy. If An SAE occurs it will also be reported to the FDA as per regulations

At each contact with the subject, the study team must seek information on adverse events by specific questioning and, as appropriate, by examination. Information on all adverse events should be recorded immediately in the source document, and also in the appropriate adverse event section of the case report form (CRF) or separate worksheet. All clearly related signs, symptoms, and abnormal diagnostic, laboratory or procedure results should recorded in the source document.

All adverse events occurring during the study period must be recorded. The clinical course of each event should be followed until resolution, stabilization, or until it has been ultimately determined that the study treatment or participation is not the probable cause. Serious adverse events that are still ongoing at the end of the study period must be followed up, to determine the final outcome.

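### Section 8.1 makes any event reported after 12 months unrelated by rule, so report date decides causality, contrary to other parts of Sections 8.1 and 8.2

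*Combined protocol and SAP*

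**What the plan says.** Under Adverse Event Reporting Period, Section 8.1 states: "For this study, the study treatment follow-up period is 12 months after enrollment". It continues: "The adverse event monitoring period will end at the end of the follow-up period". The next sentence is the one at issue: "If an event is reported after this time it would not be considered study related".

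Three other places bear on the same question:

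- **Section 8.1, Post-study Adverse Event.** At the last scheduled visit, each subject is to be told to report any later event that she or her own physician "believes might reasonably be related to participation in this study".
- **Section 8.1, definition of unanticipated problems (UPIRTSO).** An event counts as related "if it is possibly related to the research procedures". No time limit is attached.
- **Section 8.2.** "All adverse events occurring during the study period must be recorded". Each event is then followed until it resolves, stabilises, or is finally judged not to be caused by treatment or participation.

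Relatedness matters for the endpoints. Section 3.2 makes PRP-related morbidity a primary endpoint. Section 7.2 names adverse reactions and morbidity as the primary endpoints, each dichotomous, and its primary hypothesis includes the safety of PRP.

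**The concern.** A fixed end to adverse event collection is ordinary practice. This sentence goes further, because it turns the end of collection into a finding about cause. The test is the date on which the report arrives; neither onset nor clinical judgement enters. Read literally, it also covers an event that began inside the 12 months and came to light afterwards.

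Two things are at stake. The first is the classification of late safety reports: the protocol asks subjects for such reports because they may be related, and has already declared each of them unrelated. The second is the primary safety result: the rule can move an event from related to unrelated but never the other way, so any error it makes favours the treatments.

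**Working it through.** The plan gives no figure to reproduce here. The check is a comparison of the texts, followed by timing arithmetic from the study calendars in Section 6.1.

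**Step 1. What decides the matter in each place**

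| Place | Test applied | Time limit |
|---|---|---|
| 8.1, Adverse Event Reporting Period | Date of report | 12 months from enrollment |
| 8.1, Post-study Adverse Event | Subject's or physician's belief in a reasonable link | None; applies after the last visit |
| 8.1, UPIRTSO definition | Possible link to research procedures | None |
| 8.2, recording | Occurrence in the study period | By onset, not by report |
| 8.2, follow-up of an event | Resolution, stabilisation, or a judgement on cause | None by calendar |

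**Step 2. Apply the rules to the three possible cases**

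- *Onset and report both within 12 months.* All the rules can be followed together.
- *Onset within, report after* (for example, onset in month 11 and report in month 13). Section 8.2 requires the event to be recorded, and the UPIRTSO definition asks whether it is possibly related. The reporting-period sentence has already answered no. The rules conflict.
- *Onset and report both after.* The recording rule in 8.2 does not reach the event. The Post-study paragraph solicits it because it may be related, and the reporting-period sentence says it is not. The rules conflict.

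**Step 3. How often could this touch a PRP reaction?**

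Inputs: PRP at baseline and weeks 4 and 8 in Arm A, and at weeks 20, 24 and 28 in Arm B; last visit at month 12, labelled week 48 (Section 6.1). Site reactions are expected to last up to 2 to 3 days (Section 1.4). Adverse events are assessed one week after each injection and at months 3, 5, 8 and 12 (Section 6, item d).

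Time from last PRP injection to last visit:

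- Arm A: 48 − 8 = 40 weeks
- Arm B: 48 − 28 = 20 weeks

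If 12 months is read as 52 weeks, these become 44 and 24 weeks. The last one-week checks fall at week 9 (Arm A) and week 29 (Arm B). An ordinary injection-site reaction would therefore be seen long before the cut-off.

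Time from end of minoxidil (week 32 in Arm A, week 12 in Arm B) to last visit:

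- Arm A: 48 − 32 = 16 weeks
- Arm B: 48 − 12 = 36 weeks

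**Step 4. Scale of a single reclassification (illustration only)**

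Assume all 23 patients receive PRP and exactly one has a related event. The exact (Clopper-Pearson) 95% limits are:

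- One event counted: 1/23 = 4.3%. Lower limit 1 − 0.975^(1/23) = 0.1%; upper limit, the 0.975 quantile of Beta(2, 22), 21.9%.
- That event excluded: 0/23 = 0%. Upper limit 1 − 0.025^(1/23) = 14.8%.

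This shows what one event is worth at this sample size. It does not predict that one will be lost.

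**The case against.** The strongest reply is that little depends on the sentence in practice. PRP site reactions are brief and checked at one week, Section 8.2 requires specific questioning at every contact, and an event with onset before month 12 usually escapes only if it is missed at the month-12 visit or that visit does not take place. The primary endpoint is also dichotomous, so a late report changes a patient's status only if she had no earlier reaction to that treatment. All of this stands. It limits how often the rule would apply, and does not make the rule right.

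A reader might draw several stronger inferences that the documents do not support:

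- *That the rule bears unequally on the arms because follow-up after PRP is 40 weeks in one and 20 in the other.* Those windows come from the crossover calendar, not from this sentence. The minoxidil windows run the other way (16 and 36 weeks). With equal allocation (an assumption), the averages are (40 + 20)/2 = 30 weeks after PRP and (16 + 36)/2 = 26 weeks after minoxidil. The comparison is within patient, and correcting the sentence leaves the windows as they are.
- *That the safety estimate would in fact move from 1/23 to 0/23.* Section 3.4 documents site pain, swelling, redness and warmth. If these count as reactions, a total of exactly one reactor is unlikely.
- *That a late serious event would go unreported to the IRB.* Failing the related limb would change its UPIRTSO classification. Section 8.3.1, however, sends non-UPIRTSOs to the IRB as well, under a policy not reproduced in the protocol.
- *That the laboratory rule in 8.1 also contradicts 8.2.* The text reads: "A clinical laboratory abnormality should be documented as an adverse event if it was exhibited as a severe reaction". It gives a sufficient condition and does not say that no other abnormality counts. Section 8.2 separately requires clearly related abnormal laboratory results in the source document. The wording is loose, but no firm contradiction is shown.

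**Conclusion.** The sentence is wrong as written. It replaces a causality assessment with a calendar rule, and it cannot be followed together with the Post-study Adverse Event paragraph, the UPIRTSO definition of related, or the occurrence and causality tests in Section 8.2. This rests on the wording alone and needs no numerical assumption beyond the sentence being applied literally.

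The expected effect on the PRP results and on the McNemar comparison is small. The documents do not show that any true PRP reaction will be misclassified; they show that one would be if it were reported late. The practical exposure is late safety reports and events with onset before, but report after, month 12, and it applies to minoxidil as much as to PRP. The 12-month collection window itself is acceptable.

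**What to change.** Keep 12 months as the period of active collection and delete the sentence. Replace it with wording such as: *Active collection of adverse events ends at the month-12 visit. The investigator judges the relatedness of any event, whenever it is reported. Events with onset in the study period are included in the analysis if reported before database lock.*

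The plan does not mention a database lock, so Section 7.2 or 9.1 should say when it occurs. Related events with onset after the study period can be described separately, outside the between-treatment comparison.

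The change is a few sentences, with no new visits or procedures. The downside is a few more events to assess and possibly a slightly less favourable adverse event rate.

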8.3 Reporting of Serious Adverse Events and Unanticipated Problems

When an adverse event has been identified, the study team will take appropriated action necessary to protect the study participant and then complete the Study Adverse Event Worksheet and/or log. The sponsor-investigator will evaluate the event and determine the necessary follow-up and reporting required.

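### Section 8.1 settles causality by report date: events reported after month 12 are declared unrelated, yet subjects are told to report later events that may be related

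*Combined protocol and SAP*

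**What the plan says.** Section 8.1 makes three statements that bear on a late report.

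- **Adverse Event Reporting Period.** It says that "the study treatment follow-up period is 12 months after enrollment" and that adverse event monitoring stops when follow-up stops. It then says: "If an event is reported after this time it would not be considered study related".
- **Post-study Adverse Event.** At the last scheduled visit the sponsor-investigator is to tell each subject to report back any later event that she or her own physician "believes might reasonably be related to participation in this study". No end date is given.
- **UPIRTSO definition.** The term covers "Any unanticipated problem or adverse event that meets the following three criteria": serious, unanticipated and related. An event counts as related "if it is possibly related to the research procedures". No time limit is attached.

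Elsewhere, section 8.2 states "All adverse events occurring during the study period must be recorded" and "If An SAE occurs it will also be reported to the FDA as per regulations". Section 8.3 states "The sponsor-investigator will evaluate the event and determine the necessary follow-up and reporting required". The calendars in section 6.1 put the last visit at Month 12/Week 48.

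**The concern.** Ending scheduled collection at month 12 is reasonable. The sentence does something else: it assigns a causality verdict, and it does so by the date on which the report arrives. Neither onset nor clinical judgement enters. Read literally, it classes as unrelated the very reports that the Post-study Adverse Event paragraph asks for.

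What is at stake is safety classification. A possibly related event first reported after the cut-off, whatever its onset, could be labelled unrelated by rule. If it is also serious and unanticipated, it then misses the related criterion and loses UPIRTSO status. Safety is the first part of the primary hypothesis in section 7.2, so the safety section should not prejudge causality.

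**Working it through.** The plan states no figure to reproduce. The check compares the texts and then works out the timing and scale.

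**1. Do the two rules overlap?** The post-study instruction covers events after the last scheduled visit, Month 12/Week 48.

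- Week 48 = 48 × 7 = day 336. If the cut-off is that visit, every report the instruction asks for falls after it, so the overlap is complete.
- If the cut-off is 12 calendar months (day 365), the gap is 365 − 336 = 29 days, and 29 / 7 = 4.1 weeks. Only reports made in that gap escape the rule. The instruction has no end date, so the conflict remains.

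Section 5.2 equates 2 months with 8 weeks and the calendar equates month 12 with week 48. The first reading therefore fits the document better.

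**2. Does any other text set relatedness by date?** No. The UPIRTSO definition has no time limit. Section 8.2 follows each event until it resolves, stabilizes or is judged not to be caused by the study, which is a decision made event by event. Section 8.3 has the sponsor-investigator evaluate each event but does not mention causality, so it is not in direct conflict with the sentence.

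**3. How long after treatment would a new late event start?** From sections 5.2 and 6.1:

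| Last scheduled treatment | Week | Weeks before the week 48 visit |
|---|---|---|
| Arm A, last PRP injection | 8 | 48 − 8 = 40 |
| Arm A, end of minoxidil | 32 (20 + 12) | 48 − 32 = 16 |
| Arm B, last PRP injection | 28 | 48 − 28 = 20 |

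An event with onset after the last visit therefore starts at least 16 weeks after the last scheduled study treatment. That makes a related event less likely but does not exclude one. Birth defect is one of the serious categories in section 8.1, and section 4.2 excludes pregnant women because the minoxidil product is contraindicated for them. Assume birth about 38 weeks after conception. Conception during Arm A minoxidil (weeks 20 to 32) would then mean birth at about weeks 20 + 38 = 58 to 32 + 38 = 70, past either cut-off. The birth-control criterion and the week 20 pregnancy test make this unlikely.

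**4. How many reports?** The documents give no rate. Assume that a proportion p of subjects makes a late, possibly related report, with N = 23. The expected number is N × p, and the chance of at least one is 1 − (1 − p)^23.

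| Assumed p | Expected reports | Chance of at least one |
|---|---|---|
| 0.1% | 23 × 0.001 = 0.023 | 1 − 0.999^23 = 2.3% |
| 1% | 23 × 0.01 = 0.23 | 1 − 0.99^23 = 20.6% |
| 5% | 23 × 0.05 = 1.15 | 1 − 0.95^23 = 69.3% |

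Reports that are also serious and unanticipated would be fewer.

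**The case against.** The best defence is that the two statements govern different acts. One closes the study's adverse event period; the other tells subjects what to pass on. A study may receive reports and still treat them as outside its period, and the sentence may be no more than a badly worded collection cut-off. That may well have been the intention, but the words go further: they give a verdict on relatedness. If late reports are collected yet can never count as related, asking for them because they may be related serves no purpose.

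Several objections to the size of the problem do stand.

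- Section 8.2 requires recording by when an event occurs, and sends serious adverse events to the FDA with no relatedness condition stated. Section 8.3.1 covers both UPIRTSOs and non-UPIRTSOs under IRB policy. Whether losing the UPIRTSO label changes what the IRB receives, or when, depends on that policy, which is not in the documents.
- Subjects are questioned at months 3, 5, 8 and 12 and one week after each PRP injection. An event with onset during the study must be missed at those contacts before the rule can reach it. Unresolved events already identified are followed up in any case.
- The assumed rates have no anchor in the documents. They show scale only, and their range is wide.
- The section 7.2 comparison of adverse reactions and morbidity uses no causality label, so no estimate or test changes.

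**Conclusion.** The sentence is wrong as written: it fixes causality by report date and conflicts with another instruction in the same section. That conclusion rests on the text alone and holds whether month 12 means day 336 or day 365. The severity is minor. The identified harm is loss of UPIRTSO status for a late-reported event that is serious, unanticipated and possibly related. In a trial of 23 subjects, such events should be rare. The expected counts depend wholly on the assumed rates, and they count all late, possibly related reports rather than that narrower group.

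**What to change.** Delete the sentence from Adverse Event Reporting Period in section 8.1 and put in its place:

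> Scheduled collection of adverse events ends at the Month 12/Week 48 visit. Events reported later are recorded by onset date, and the sponsor-investigator assesses their relatedness by the same criteria as earlier events.

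This also settles whether the cut-off is the week 48 visit or the calendar anniversary. The cost is one sentence removed and two added. No visits are added, because subjects are already asked to report later events to the sponsor-investigator, and the sample size and planned analysis do not change. The only downside is a little assessment work for any late report that arrives.

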8.2 Recording of Adverse Events

All adverse events will be documented as required under 21 CFR part 1271. Depending on the nature and seriousness of the adverse reaction, the IRB will be notified according to the Mayo Clinic IRB policy. If An SAE occurs it will also be reported to the FDA as per regulations

At each contact with the subject, the study team must seek information on adverse events by specific questioning and, as appropriate, by examination. Information on all adverse events should be recorded immediately in the source document, and also in the appropriate adverse event section of the case report form (CRF) or separate worksheet. All clearly related signs, symptoms, and abnormal diagnostic, laboratory or procedure results should recorded in the source document.

All adverse events occurring during the study period must be recorded. The clinical course of each event should be followed until resolution, stabilization, or until it has been ultimately determined that the study treatment or participation is not the probable cause. Serious adverse events that are still ongoing at the end of the study period must be followed up, to determine the final outcome.

